## **List of Tables**

Table 1: Summary of Blood Sample Collection

Table 2: Summary of follow up

1.	Title:	Randomized, Quadruple-blind, Placebo-controlled, Clinical Trial to determine the effects of Coffee (caffeine) supplementation on Hepatic Steatosis and Fibrosis in Metabolic dysfunction-associated Steatotic Liver Disease(MASLD)
2.	Objective	
 
Primary Objective:         
 
To assess the effect of coffee (caffeine) supplementation on hepatic steatosis and fibrosis in NAFLD patients measured by CAP score using Fibro scan and Hepatic fibrosis measured by TE using Fibro scan and FIB-4 score
 
 
 
Secondary Objectives:         
 
To assess changes in liver enzymes (ALT, AST, GGT) with caffeine supplementation.
 
To assess the impact on metabolic markers(HbAIC, lipid profile, BMI).
 
To assess potential side effects of caffeine supplementation.
 
 
 

3.	Study design	Randomized, Quadruple blinded, Placebo-controlled
4.	Study setting	Gastroenterology Clinic, University Medical Unit, Colombo North Teaching Hospital, Ragama, Sri Lanka.
5.	Study population	Patients attending the clinic
6.	Definition of intervention/main exposure variable	
7.	Definition of primary outcome	Is the reduction in hepatic steatosis and fibrosis in non-alcoholic fatty liver disease (NAFLD) patients which is measured by Liver stiffness measurement (LSM) via Fibro scan, Controlled attenuation parameter (CAP) scores via Fibro scan and FIB-4 score calculation. All comparisons will be from baseline to week 24.
8.	Sample size	110 participants
9.	Data collection method	It would be conducted by two MBBS-qualified researchers trained in the study protocol.  Interviewer-administered questionnaires will collect demographic and clinical data.  Case Report Forms (CRFs) will document medical history, anthropometric measurements, clinical findings and investigation findings.  Monthly follow-ups will include:  • Physical exams, monitoring of adherence, side effects, and lifestyle factors (diet, exercise, alcohol intake)  In 3 months and 6 months  • Blood investigations, fibro scan and US scan findings
10.	Proposed data analysis	Data will be analyzed using SPSS software version 21
11.	Main ethical issues	Informed consent: Obtained twice (for eligibility and enrollment).  Confidentiality: Participants' personal data will be anonymized.  Risk-benefit balance: Potential side effects of caffeine (e.g., palpitations, insomnia, high blood pressure) will be monitored.  Adverse events reporting: Participants can report symptoms anytime, and serious adverse events will be immediately reported to relevant authorities.

28.02.2025

## 1. Introduction and Literature Review

Non-alcoholic fatty liver disease (NAFLD) is an increasingly prevalent clinical disorder and a public health concern, significantly contributing to the global burden of chronic liver disease(1). It has emerged as the leading cause of chronic liver disease worldwide and is associated with serious complications, including fibrosis, cirrhosis, and hepatocellular carcinoma (HCC)(2).

NAFLD is characterized by abnormal lipid deposition in the liver and is diagnosed when hepatic steatosis is present in >5% of hepatocytes, as confirmed by liver biopsy, without secondary causes of liver injury or excessive alcohol intake(3). It has also been strongly associated with metabolic disorders such as type 2 diabetes mellitus, obesity, and insulin resistance and has the potential to progress to non-alcoholic steatohepatitis (NASH), fibrosis, cirrhosis, and ultimately HCC, increasing both morbidity and mortality among affected individuals(2,3).

The pathogenesis of NAFLD and its progression to NASH is complex and not yet fully understood, but it is widely recognized as a two-step process. The first step involves hepatic fat accumulation (steatosis), where lipid deposition in hepatocytes occurs due to increased fat synthesis, decreased lipid export, and impaired mitochondrial function. The second step consists of cellular and molecular changes leading to inflammation and fibrosis, driven by the oxidation of fatty acids, which induces oxidative stress and triggers cytokine-mediated injury, immune system dysregulation, mitochondrial dysfunction, lipotoxicity, and chronic inflammation. These mechanisms contribute to the progression from NAFLD to advanced fibrosis(4,5). Both genetic predisposition and environmental factors influence disease progression(6).

It affects nearly 38% of the global population, and its prevalence is increasing—particularly among younger individuals who are being exposed to risk factors such as poor dietary habits, sedentary lifestyles, and obesity at an earlier age(7). In addition, improving socioeconomic status in low-income regions has led to an increased availability of calorie-dense, unhealthy foods, further exacerbating the rise in NAFLD cases(8). This prevalence also parallels the increasing incidence of cirrhosis, cirrhotic complications, and HCC, which adds to the global healthcare burden(9).

28.02.2025

#### 1.1. Benefits of Caffeine to health

Coffee is one of the most widely consumed beverages worldwide and has been associated with numerous health benefits, including a reduced risk of type 2 diabetes, Parkinson's disease, prostate cancer, hepatitis C, and HCC(10,11,12). Large-scale epidemiological studies have shown that increased coffee consumption is linked to a modest reduction in all-cause mortality(13).

#### 1.2. Supplementation of Caffeine in Liver conditions

Specifically, coffee has demonstrated beneficial effects on liver-related conditions. Regular coffee consumption has been linked to a reduced risk of cirrhosis and chronic liver disease, a lower severity of viral liver diseases (e.g., hepatitis C) and decreased levels of liver enzymes (ALT, GGT, bilirubin), indicating improved liver function(14,15).

These protective mechanisms of coffee are thought to stem from its antioxidant, anti-inflammatory, and anti-adipogenic properties (16). Coffee consumption has been associated with reduced production of reactive oxygen species (ROS), inflammatory cytokines (TNF- $\alpha$ , TGF- $\beta$ ), and oxidative stress, thereby protecting hepatocytes from damage(17). It has also been associated with the inhibition of hepatic stellate cell activation, thereby reducing liver fibrosis(18). Moreover chlorogenic acids, which is a constituent of coffee, also improve glucose metabolism, reduce insulin resistance, and help mitigate the risk of NAFLD progression(19).

Several studies have suggested an inverse relationship between coffee consumption and NAFLD prevalence and severity. A study reported that individuals who drank coffee regularly had a 29% reduced risk of developing NAFLD and a 30% lower risk of liver fibrosis in NAFLD patients compared to non-coffee drinkers(20,21). Experimental studies have also shown that coffee upregulates mitochondrial and endoplasmic reticulum (ER) chaperone proteins, such as glucose-related protein 78 (GRP78), which modulates ER homeostasis and prevents metabolic stress-induced liver injury(22). Coffee's polyphenols, which have a structure similar to silymarin (a known hepatoprotective compound), can increase the production of antioxidant proteins such as periredoxin-1 (PRDX-1), which helps counteract oxidative damage in hepatocytes(23).

28.02.2025

Additionally, non-caffeine components of coffee, such as cafestol, kahweol, and chlorogenic acid, have been shown to reduce triglyceride and cholesterol deposition in hepatocytes. And prevent hepatocellular carcinoma development(24).

## 2. Hypothesis, Objectives, Outcomes and End points

## 2.1. Hypothesis:

- **Null Hypothesis**: Coffee (caffeine) supplementation has no effect on hepatic steatosis and fibrosis in NAFLD patients.
- Alternative Hypothesis: Coffee (caffeine) supplementation reduces hepatic steatosis and fibrosis in NAFLD patients.

## 2.2. Objectives:

#### **Primary Objective:**

To assess the effect of coffee (caffeine) supplementation on hepatic steatosis and fibrosis
in NAFLD patients measured by CAP score using Fibro scan and Hepatic fibrosis
measured by TE using Fibro scan and FIB-4 scores

#### **Secondary Objectives:**

- To assess changes in liver enzymes (ALT, AST, GGT) with caffeine supplementation.
- To assess the impact on metabolic markers(HbAIC, lipid profile, BMI).
- To assess potential side effects of caffeine supplementation.

#### 2.3. The Outcomes:

#### • Primary Outcome

The primary outcome is to compare the reduction of Hepatic steatosis measured by CAP score using Fibro scan and Hepatic fibrosis measured by TE using Fibro scan and FIB-4 scores

#### Secondary Outcome

The secondary outcome is to compare the reduction of AST and ALT levels

28.02.2025

#### 2.4. End Points:

#### **Primary endpoints**

- 1. Reduction in Liver stiffness measurement (LSM) as determined by fibroscan of liver from baseline to week 24.
- 2. Reduction in Hepatic steatosis with controlled attenuation parameter (CAP) as determined by fibroscan from baseline to week 24.
- 3. Reduction in Fib-4 score as determined by calculation from baseline to week 24.

#### **Secondary endpoints**

- 1. Reduction in Anthropometric parameters: waist circumference, weight and body mass index (BMI) from baseline to week 24.
- 2. Reduction in levels of Aspartate Transaminase (AST), Alanine Transaminase (ALT) and Gamma Glutamyl Transpeptidase (GGT) from baseline to week 24.
- 3. Reduction in fatty liver index (FLI) from baseline to week 24.

#### **Exploratory endpoints**

- 1. Changes in Lipid profile as determined by total cholesterol (TC), triglycerides (TG), high density lipoproteins (HDL) and low-density lipoproteins (LDL) from baseline to week 24.
- 2. Changes in Metabolic parameters: (FBS) and (HbA1c) from baseline to week 24.
- 3. Changes in Beta cell function using HOMA-IR from baseline to week 24.

28.02.2025

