#### 4.3.1. Inclusion Criteria

- Both male and non-pregnant, non-lactating female patients aged 18 65 years who provide written informed consent before starting the study
- Patient diagnosed with type 2 diabetes based on American Diabetes Association (ADA) definition or who only take oral antidiabetic drug.
- CAP score >263
- Fulfilling 2/3 USS criteria for fatty liver

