#### 4.3.2. Exclusion Criteria

- History of unsafe alcohol consumption
- Other liver disease (chronic viral/autoimmune/hereditary)
- Use of steatogenic medications
- History of drug dependence
- Body mass index (BMI) ≥35 kg/m2

28.02.2025

- A restrictive diet or weight change  $\geq 5$  kg during the 3 months prior to study
- Pregnancy or lactation
- Patients with sensitivity to caffeine intake
- Patients with symptomatic ischaemic heart disease, arrythmia's
- Any condition that, in the opinion of the clinician, would contraindicate the patient's participation.

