#### Collection of blood samples

• Table 1 summarizes the blood sample collection. The investigations will be done at the North Colombo Teaching hospital which is an accredited laboratory. These tests are required to assess the efficacy and safety of the medications in an objective manner.

Table 1: Summary of Blood Sample Collection

Day	Blood volume	Investigations
Enrolment	6 ml	FBS, Liver profile  Lipid profile, Serum HCG (Female participants only)
Allocation Visit - Beginning of 1 st Month	6 ml	FBS Serum HbA1c Fasting serum insulin

28.02.2025

		Lipid profile, Liver profile, Total bilirubin
		Serum creatinine
		FBC
		Serum electrolytes
3 rd month and 6 th month	6 ml	FBS
		Serum HbA1c
		Fasting serum insulin
		Lipid profile, Liver profile, Total bilirubin
		Serum creatinine
		FBC
		Serum electrolytes

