## 5.1. Lifestyle modification and standard care during the study period

There is currently no approved pharmacological treatment which can reverse NAFLD or control disease progression. Hence current treatment strategies are focused on lifestyle modifications. All patients in the two groups will receive standard diet modification and exercise and physical activity recommendations according to Clinical Practice Guidelines developed by Sri Lanka College of

28.02.2025

Endocrinologists, Sri Lanka society of Gastroenterology, 2019. However, management of comorbid conditions such as diabetes and hypertension will be as per routine hospital practice based on guidelines. If patients are already on pharmacological treatment for NAFLD, such patients will not be recruited to study.

Before recruitment all participants will be made aware of the required lifestyle modification during the study period as per standard management schedule.

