#### 5.5. Follow up assessment

The recruited patients will be advised to come for monthly assessments and will be asked to attend the nearest hospital, if they develop any complications and inform the study team of such incidence.

The degree of adherence to prescribed lifestyle changes and diet will be recorded at the baseline and monthly follow-up visits. Physical activity and alcohol consumption will also be monitored at the baseline and monthly follow-up visits.

Anthropometric measurements, physical examination and vital sign measurements (BP, HR, RR etc..) will be monitored at the baseline and each monthly visit. Details on concomitant medications will be recorded in monthly visits.

Liver profile, Lipid profile, Full blood count, Serum creatinine, fasting blood glucose, HbA1c, serum insulin, serum electrolytes and urine analysis and serum insulin will be investigated at the baseline, at 3 months and 6 months.

Fibro scan will be done at the baseline and after 6 months at the completion of the study.

The details of items which will be measured on every visit are described in Table 2.

Table 2: Summary of follow up

	Enrolment	Allocation 1	Subsequent visits							
TIME POINT		0	1 st	2 nd	3 rd	4 th	5 th	6 th		
			mont	mont	month	mont	month	mont		
			h	h		h		h		
ENROLMENT										
Eligibility screen	×									
Informed consent	×									
Allocation		×								
INTERVENTIO										
NS										
caffeine or		×	×	×	×	×	×			
placebo										
ASSESSMENTS										
Medical history	×	×	×	×	×	×	×	×		
taking										
AUDIT	×	×	×	×	×	×	×	×		
FFQ and IPAQ	×	×	×	×	×	×	×	×		

Height, weight			×	×	×	×	×	×
and waist								
circumference								
Blood pressure	×	×	×	×	×	×	×	×
Physical examination 	×	×	×	×	×	×	×	×
USS scan	×							
Fibro scan		×						×
FBG	×	×			×			×
Fasting serum insulin		×			×			×
HCG only female	×							
Serum HbA1c		×			×			×
Lipid profile	×	×			×			×
Liver enzymes	×	×			×			×
Total bilirubin	×				×			×
Serum creatinine		×			×			×
Serum electrolytes		×			×			×

FBC	×		×		×
UFR	×		×		×

28.02.2025

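### HOMA-IR is planned from fasting serum insulin in a trial whose wording admits insulin-treated participants, in whom the index does not validly reflect insulin resistance

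*Protocol*

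**What the plan says.** Protocol section 2.4 lists as its third exploratory endpoint "Changes in Beta cell function using HOMA-IR from baseline to week 24". The insulin input is "Fasting serum insulin", which Table 1 (section 4.6) and Table 2 (section 5.5) schedule at allocation, month 3 and month 6, together with fasting glucose. C-peptide appears in neither table.

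Four passages decide whether insulin users can be in the trial:

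- Section 4.3.1, diabetes criterion: "Patient diagnosed with type 2 diabetes based on American Diabetes Association (ADA) definition or who only take oral antidiabetic drug".
- Section 4.3.2, the only exclusion naming a class of current medicines: "Use of steatogenic medications". Insulin is not named.
- Section 5.1, a further bar on recruitment: "If patients are already on pharmacological treatment for NAFLD, such patients will not be recruited to study". This does not reach glucose-lowering treatment.
- Section 5.1, care during the trial: "management of comorbid conditions such as diabetes and hypertension will be as per routine hospital practice based on guidelines".

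Section 5.5 adds: "Details on concomitant medications will be recorded in monthly visits". No use of that record is tied to HOMA-IR. Section 4.8 gives tests for CAP and LSM and for the secondary endpoints, repeated measures ANOVA for variables it does not list, and use of the last available value for participants lost to follow-up. It does not mention HOMA-IR or the exploratory endpoints.

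**The concern.** HOMA-IR is the product of two fasting measurements. It works as an index of insulin resistance because, in someone making their own insulin, a high insulin level at a given glucose means the tissues respond poorly. In someone injecting insulin, the measured level may include the drug, and the body's own output and the glucose are both altered by treatment. The product then partly records what was prescribed. Without C-peptide, own and injected insulin cannot be separated afterwards.

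There are two routes into the data: a participant may enter on insulin, or may start or change it in the six months after randomisation. The second route stays open however the diabetes criterion was meant.

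At stake is the interpretability of one exploratory endpoint. This is separate from the endpoint's label, which calls HOMA-IR a measure of beta cell function; correcting the label would leave the problem in place.

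**Working it through.** **No plan figure to reproduce.** The protocol gives no HOMA-IR formula, expected value, SD, assay or share of insulin users. Everything below is illustrative.

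**Formula (assumed).** HOMA-IR = fasting insulin (uU/mL) x fasting glucose (mg/dL) / 405.

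**Step 1. Scenario in which the assay detects injected insulin.** Assumed baseline: insulin 15, glucose 150.

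- Baseline: 15 x 150 / 405 = 5.56.
- After a start, insulin 25, glucose 120: 25 x 120 / 405 = 7.41, change +1.85 (33%).
- Insulin 30, glucose 120: 30 x 120 / 405 = 8.89, change +3.33 (60%).
- Insulin 40, glucose 110: 40 x 110 / 405 = 10.86, change +5.31 (96%).

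Glycaemia improves in each case while the index worsens.

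**Step 2. When does the index rise at all?** From this baseline, measured insulin must exceed 15 x 150 / 120 = 18.75 at glucose 120, or 15 x 150 / 110 = 20.5 at glucose 110. The cases in step 1 all lie above these limits, so they show one side only.

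**Step 3. Letting detection vary.** Assumed baseline: insulin 12, glucose 150, so HOMA-IR = 12 x 150 / 405 = 4.44. After a start, glucose is 120, the body's own insulin is 8, and the assay picks up a further x uU/mL, so HOMA-IR = (8 + x) x 120 / 405.

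| x detected | HOMA-IR | Change |
|---|---|---|
| 0 | 2.37 | -2.07 |
| 5 | 3.85 | -0.59 |
| 10 | 5.33 | +0.89 |
| 20 | 8.30 | +3.85 |
| 40 | 14.22 | +9.78 |

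The sign depends on the assay and on the insulin present at sampling.

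**Step 4. Effect on an arm mean.** Suppose one arm has three more insulin starts than the other. Section 4.4 gives 55 per arm; if the whole 20% dropout allowance is used, 55 x 0.8 = 44 remain.

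- Step 1 values, 55 per arm: 3/55 x 1.85 = 0.10 to 3/55 x 5.31 = 0.29.
- Step 1 values, 44 per arm: 3/44 x 1.85 = 0.13 to 3/44 x 5.31 = 0.36.
- Step 3 values, 55 per arm: 3/55 x (-2.07) = -0.11 with none detected; 3/55 x 3.85 = 0.21 with 20 detected; 3/55 x 9.78 = 0.53 with 40 detected.

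Without an SD for HOMA-IR, none of these can be called large or small.

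**The case against.** The strongest objection is that whose HOMA-IR counts, and what happens after a treatment change, are details that a statistical analysis plan commonly settles, and that plan is not shown. This stands in part: a rule may exist there. But the eligibility wording, the routine-care rule and the choice of serum insulin without C-peptide are fixed in the protocol, and together they create the problem.

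Second, the word limiting the second limb of the diabetes criterion to oral treatment suggests that insulin users were never meant to enter. That is plausible, and clearer wording could close the baseline route. It would not close the route through insulin started under routine care.

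Third, three stronger readings are tempting, and the documents do not support them:

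- A reader might infer that anyone who starts insulin and improves is recorded as more insulin resistant. That needs an assay that detects enough injected insulin; the assay is not named, and step 3 shows falls as well as rises.
- A reader might infer that the comparison of arms is biased. Allocation is randomised and blinded (section 4.7), so a chance excess of starts in one arm is noise. A systematic difference would arise if, for example, caffeine altered glycaemia, which is an open question here; the distortion would then not be unrelated to treatment.
- A reader might infer that section 4.8 prescribes one analysis of HOMA-IR for everyone. It does not mention the endpoint. It does allow the Mann-Whitney test for the comparisons it names, which would blunt a few extreme values if used here.

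**Conclusion.** The point holds as a validity problem for one exploratory endpoint. As worded, the protocol allows insulin-treated participants, and in them HOMA-IR from serum insulin does not validly reflect insulin resistance. The main consequence is added noise. The contrast between arms is distorted only if insulin starts or changes differ by arm, and then in a direction that cannot be stated in advance.

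The size is unknown because the share of insulin users, the assay and the HOMA-IR SD are not given. The shifts in step 4 rest wholly on assumed insulin and glucose levels and on an assumed excess of three starts, and the sign reverses if little injected insulin is detected. The primary and secondary conclusions do not depend on this endpoint. It is a cheap improvement, not a threat to the trial.

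**What to change.** Add a short rule for HOMA-IR to section 4.8:

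1. Analyse HOMA-IR in participants not using insulin at baseline, identified from the drug history and the concomitant-medication record, and report the number excluded per arm. Baseline use precedes randomisation, so this restriction keeps the randomised comparison intact.
2. Report the number per arm who start insulin after randomisation, and give the HOMA-IR result both with and without their values after the start, as a sensitivity analysis. Deletion should not be the only analysis, because it selects on an event after randomisation that is probably related to worsening glycaemia.
3. Do not carry an insulin-affected value forward. Under the last-available-value rule, a month-3 value drawn on insulin could otherwise stand in for month 6.

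Separately, the investigators should reconcile the two limbs of the diabetes criterion in section 4.3.1 so that it is clear whether insulin users are eligible. Which way that goes is for them to decide.

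The cost is a few sentences and slightly fewer participants for an exploratory endpoint. No new sampling is needed, since the medication data are already planned.

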#### **Final Sample Size**

- 55 participants per group
- Total: 110 participants (both groups combined)

28.02.2025

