#### Laboratory investigations

Serum fasting plasma glucose, Lipid profile, Liver enzymes will be done to assess the
baseline fasting blood glucose for recruitment into the study to comply with inclusion
criteria. Serum HCG will be tested for female participants to exclude pregnancy.
Abdomen ultrasound scan will be performed to assess eligibility to the study.

28.02.2025

After recruitment baseline testing will be done for HbA1c, serum Insulin level, fasting
plasma glucose, Lipid profile, Liver enzymes. Serum creatinine, full blood count, serum
electrolytes and urine analysis will be done for safety assessments.

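### Exploratory endpoint 3 names beta cell function but specifies HOMA-IR, an insulin-resistance index, so as written it cannot support a statement about beta cell function

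*Protocol*

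**What the plan says.** Section 2.4 of the protocol has a short list headed "Exploratory endpoints". Its third item is "Changes in Beta cell function using HOMA-IR from baseline to week 24". This is the only place in the available text where either HOMA or beta cell function appears. The protocol gives no formula, no beta-cell index and no separate insulin-resistance endpoint.

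The inputs for a homeostasis index are collected. Table 1 in Section 4.6 lists "Fasting serum insulin" beside fasting blood sugar at the allocation visit and at months 3 and 6. The list of tests in Section 5.5, which also includes fasting blood glucose, continues "HbA1c, serum insulin, serum electrolytes and urine analysis and serum insulin will be investigated at the baseline, at 3 months and 6 months". The case report form has entries for fasting blood sugar (in mg/dL) and fasting serum insulin, and none for a derived index.

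The introduction mentions insulin resistance but not beta cell function. Section 1 links NAFLD with "type 2 diabetes mellitus, obesity, and insulin resistance". Section 1.2 says that chlorogenic acids in coffee "also improve glucose metabolism, reduce insulin resistance, and help mitigate the risk of NAFLD progression".

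**The concern.** The IR in HOMA-IR stands for insulin resistance. The endpoint therefore joins one construct to an index of another, and it does so in an operative endpoint definition, not in background text. An analyst who follows the line will calculate HOMA-IR correctly and file the result under a heading that it does not measure.

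What is at stake is interpretation. If a given change in HOMA-IR always implied the same change in beta cell function, the label would be loose but harmless. If the same fall in HOMA-IR can go with a rise or a fall in an index of beta cell function, the named index cannot answer the named question.

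**Working it through.** The protocol states no figure for this endpoint, so there is none to reproduce. The check is whether the direction of change in HOMA-IR fixes the direction of change in a beta-cell index.

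**Inputs**
- Construct and index: Section 2.4, exploratory endpoint 3.
- Formulae: the standard homeostasis definitions, taken as an assumption. With glucose G in mmol/L and insulin I in mU/L, HOMA-IR = G × I / 22.5 and beta-cell index = 20 × I / (G − 3.5).
- Glucose and insulin values: assumed for illustration, not trial data.

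**Starting point, G = 8 and I = 15**
- HOMA-IR = 8 × 15 / 22.5 = 5.33
- Beta-cell index = 20 × 15 / 4.5 = 66.7

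**Case A: glucose falls to 7, insulin stays at 15**
- HOMA-IR = 7 × 15 / 22.5 = 4.67, a change of −12.5%
- Beta-cell index = 20 × 15 / 3.5 = 85.7, a change of +28.6%
- The numbers move in opposite directions, but both changes are favourable: less resistance and a higher beta-cell index.

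**Case B: insulin falls to 12, glucose stays at 8**
- HOMA-IR = 8 × 12 / 22.5 = 4.27, a change of −20%
- Beta-cell index = 20 × 12 / 4.5 = 53.3, a change of −20%
- HOMA-IR looks better while the beta-cell index drops. This is the case in which a misreading does harm.

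**Same check in mg/dL, the glucose unit on the case report form.** Here HOMA-IR = G × I / 405 and beta-cell index = 360 × I / (G − 63).

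| Glucose (mg/dL) | Insulin | HOMA-IR | Beta-cell index |
|---|---|---|---|
| 130 (start) | 15 | 4.81 | 80.6 |
| 115 | 15 | 4.26 | 103.8 |
| 130 | 12 | 3.85 | 64.5 |
| 135 | 11 | 3.67 | 55.0 |

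HOMA-IR is below its starting value in all three later rows. The beta-cell index is above its starting value in one row and below it in two.

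The formulae show that this does not depend on the chosen values. With insulin fixed, HOMA-IR increases with glucose while the beta-cell index decreases with it (for glucose above 3.5 mmol/L), so the two move in opposite directions. With glucose fixed, both are proportional to insulin and move together.

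**The case against.** The strongest reply is that this is a labelling slip in the last of three exploratory items, and that no wrong conclusion is written anywhere. A reader might infer that the trial will report a fall in HOMA-IR as a beta-cell effect. The protocol does not say so. Beta cell function and HOMA-IR are absent from the hypothesis, objectives and outcomes, and the data analysis section (4.8) does not name this endpoint. The line itself names HOMA-IR, so a report that followed it would show which index was used. This part of the reply stands: a wrong conclusion is a risk, not a stated intention.

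A reader might also take opposite movement of the two indices as the harm. It is not. In Case A both changes are favourable, so reading the fall as a beta-cell benefit would not reverse the verdict. Only falling insulin, as in Case B, produces a real misreading.

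Finally, a reader might infer from the introduction that insulin resistance was meant and that the words on beta cell function are the slip. The text does not settle this. The sentence in Section 1.2 concerns chlorogenic acids, whereas the tablets contain caffeine anhydrous (Section 5). Section 1 mentions insulin resistance only as an associated disorder. The index could equally be the slip.

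One reply does not stand, namely that the matter can be left to a statistical analysis plan. Such a plan can add a formula, but here it would have to depart from either the construct or the index that the protocol names.

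**Conclusion.** Exploratory endpoint 3 is wrong as written, with low severity. It pairs beta cell function with an index of insulin resistance, so it cannot support a statement about beta cell function and could be misread. In the illustration, a fall in HOMA-IR of 12.5% goes with a 28.6% rise in the beta-cell index, and a fall of 20% goes with a 20% drop.

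The mismatch rests on the wording of the endpoint alone. The sizes rest on the standard homeostasis formulae and on assumed glucose and insulin values, so they show that the direction is not determined and do not predict any result of this trial. The primary endpoints, alpha and the sample size of 110 are unaffected.

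**What to change.** Before unblinding, the sponsor should state which construct is intended and make label and index agree. Any of these would do:
- change in insulin resistance (HOMA-IR) from baseline to week 24;
- change in beta cell function (HOMA beta-cell index) from baseline to week 24;
- both, listed as two separate exploratory endpoints.

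The formula and its units should be given with the endpoint, since glucose is recorded in mg/dL.

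The cost is a line or two of wording. Either index comes from the fasting glucose and fasting insulin already scheduled at baseline, 3 months and 6 months, so no new samples, visits or participants are needed. Settling it before unblinding keeps the choice of construct independent of the results.
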